Appendix: SMS Run-In: Drink Driving

Day & Time	Incoming	Outgoing
Enrollment		Hi [_NAME_]. Welcome to to the SaVE Study For the next 2 weeks, each Sunday, we will ask you about your seatbelt use in the past week If you complete at least 50% of the text queries, you will be eligible for the rest of the study
	Any response	If at any time you wish to stop receiving texts, just text us "stop"
	•	
Sunday, 4pm		Hi [_NAME_], it's theSaVE Team checking in How often have you driven a car the past week? 0=never; 1=a few times; 2=most days; 3=every day
2 hours	[Missing] x1 [Missing]	We missed your response. Text us how often you have been a passenger or driver in a car the past week?
2 hours	x2 [Nonsense]	You must be busy. We will check in next week We don't understand. Please text us a response option: 0=never; 1=a few times; 2=most days; 3=every day
	0 1,2,3 [Missing]	OK Have you driven a vehicle within 3 hours after consuming 3 or more alcoholic drinks?
1 hour	x1 [Missing]	We missed your response. Text us Yes or No.
1 hour	x2 [Nonsense	You must be busy. We will check in next week
]	We don't understand. Please text us either Yes or No
	No	Thanks
Day 15		
Day 15 (Monday)		Due to your low response rate, you will be withdrawn from the SaVE Study
,		For further information about safe vehcile use, go to www.NHTSA.gov

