2.3 Inclusion criteria

Inclusion criteria:

- 1) Adult participant (age \geq 18 years & \leq 25 years)
 - a. Cohort 1: Any vehicle trip in past 2 weeks where individual reports not using a seat belt
 - b. Cohort 2: Any vehicle trip in past 2 weeks where individual reports phone was used to type while driving and car was moving
 - c. Cohort 3: Any vehicle trip in past 2 weeks where individual reports driving a vehicle within 3 hours after consuming 3 or more drinks

Exclusion criteria:

- 1) Member of a protected population (prisoner)
- 2) Unable to provide informed consent
- 3) No plan to drive and/or ride in a vehicle in the next month
- 4) Non-English speaking
- 5) No personal mobile phone or planning on changing phone in next 3 months

Justification of Inclusion and Exclusion Criteria: The inclusion criteria were chosen to isolate three different vehicle risk behaviors in a population with high risk of injuries due to these risks. We chose to be more inclusive than restrictive in these criteria to ensure me meet enrollment goals in the allotted time of funding. The exclusion criteria were chosen to minimize the risk of potential harm to vulnerable populations.

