4.2.3 Secondary Analyses

The percentage of ED patients who screen positive and agree to enroll, the percentage of ED patients who enroll who meet run-in criteria, the percentage of ED patients enrolled in the Intervention arm who complete at least 50% of the SMS assessments during the intervention period, and the percentage of ED patients enrolled in the Intervention arm who found the program helpful will be calculated and presented with 95% confidence intervals. We will explore whether individual factors (e.g. sex, race, education) are associated with enrolling, meeting run-in criteria, completing SMS assessments or finding the program helpful using multi-level modeling. We will examine whether perceived norms, perceived control, or perceived risk differed between treatment arms. We will explore the slope of change over time in SMS risk reports using generized estimating equations (GEE) with log link function, examining time, treatment and time*treatment effects. Any individual factors signifianctly associated with SMS assessment completion will be included as

covariates.GEE is the recommended technique to handle non-parametric residuals and missingness associated with repeated-measured data. We will use robust estimates and account for clustering of outcome data within individuals. Results will be presented as odds ratios with 95% confidence intervals.

Handling Missing Outcome Data: If a participant is missing outcome assessment time points (week 8 or week 14), vehicle risk behavior will be imputed based on a pre-defined plan as follows. If a participant has reported that risk via SMS weekly reports, we will use those values for missing weeks. If either of the prior 2 weeks is missing on both web-based recall report or SMS reports, we will impute the missing week based on the worst performance recorded in the weeks either before or after the missing one using SMS values. We believe that this will provide the most conservative estimate of the missing value. Sensitivity analyses will be performed using various other imputation techniques, including multiple chained imputations using baseleine and prior SMS reports.

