Appendix: Screening Questions

Question	How old are you?	18 years old	19 years old	20 years old	21 years old
Code	age	0	1	2	3
Question	What is your sex?	Female	Male		
Code	sex	0	1		
Question	Are you Hispanic or Latino?	No	Yes		
Code	hisp	0	1		
Question	What is your race? (Select one or more responses.)	Black or African American	White	Asian	Other
Code	brace, wrace, asian, rother	0/1	0/1	0/1	0/1
Question	Are you currently enrolled in school?	No	Yes, High School	Yes, College	
Code	school	0	1	2	
	The following questions ask you to recall times you have been in a car over the past 2 weeks.				
Question	How often have you driven a car?	Never	A few times	Most	Every
Code	driver	0	1	days 2	day 3
Question	How often did you wear a seat belt when you drove a car?	Never	A few times	Most of the time	Always
Code	drive_seatbelt	0	1	2	3
Question	How often have you been a passenger in the front seat of a car?	Never	A few times	Most days	Every day
Code	pass_front	0	1	2	3
Question	How often did you wear a seat belt when you were a passenger in the front seat ?	Never	A few times	Most of the time	Always
Code	pass_seatbelt1	0	1	2	3
	How often have you been a passenger in the back seat of a car?	Never	A few times	Most days	Every day
	pass_back	0	1	2	3
	How often did you wear a seat belt when you were a passenger in the back seat?	Never	A few times	Most of the time	Always
	pass_seatbelt2	0	1	2	3
Question	How often did you type on your phone while you were driving and when the car was moving?	Never	A few times	Most of the time	Always
Code	distract	0	1	2	3
Question	Have you driven a vehicle within 3 hours after consuming 3 or more alcoholic drinks?	No	Yes		
Code	drinks	0	1		
	Thanks! Please hand the iPAD back to the Researcher.				

RA enters code: SAVE

Program displays which risks+

Script RA tells pt they are potentially eligible for study or thanks them for their time.

If eligible pt interested, RA asks the following:

Question	Do you have a personal cell phone with text messaging ?	No	Yes
Code	sms	0	1
Question	Do you plan to drive and/or ride in a vehicle in the next month?	No	Yes
Code	future	0	1
Question	Do you plan to change phone numbers in the next 3 months?	No	Yes
Code	phone	0	1

Logic If sms=0 or future=0 or phone=1, they are excluded.

RA either thanks them for their time or starts informed consent.

RA goes to WebDataXpress site

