	How often have you driven a car the past week? 0=never; 1=a few times; 2=most days; 3=every day
[Missing] x1	We missed your response. Text us how often you driven a car the past week?
[Missing] x2	You must be busy. We will check in tomorrow
[Nonsense]	We don't understand. Please text us a response option: 0=never; 1=a few times; 2=most days; 3=every day
0	ОК
1,2,3	Have you driven a vehicle within 3 hours after consuming 3 or more alcoholic drinks?
[Missing] x1	We missed your response. Text us whether you have driven within 3 hours of drinking 3 or more alcoholic beverages.
[Missing] x2	You must be busy. We will check in next week
[Nonsense]	We don't understand. Please text us Yes or No.
No	[Posiitve Reinforcement Message]
Yes	[Social Norms Message]
Goal met	[Goal Met Message]
Goal not met	[Goal Not Met Message]
	Would you be willing to commit to a goal to not drive after drinking this week?
[Missing] x1	We missed your response. Text us whether you'd be willing to set a goal?
[Missing] x2	You must be busy. We will check in next week
[Nonsense]	We don't understand. Please text us either yes or no
No	[No Goal Roll Library Message]
Yes	[Goal Reinforcement Message]

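### The weekly text that records Cohort 3's drink-driving risk has no reference period of its own, which leaves a Yes ambiguous for participants who all reported the behaviour before entry

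*Combined protocol and SAP*

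**What the plan says.** **The item.** Appendix: SMS Run-In: Drink Driving records the weekly risk with "Have you driven a vehicle within 3 hours after consuming 3 or more alcoholic drinks". The drink-driving intervention script uses the same wording. The run-in reminder asks only for a Yes or No. The intervention reminder says "Text us whether you have driven within 3 hours of drinking 3 or more alcoholic beverages". None of these gives a period.

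**What surrounds it.** The text just before it asks "How often have you driven a car the past week". An answer of 0 ends the exchange, and 1, 2 or 3 leads to the risk item. The Cohort 3 run-in welcome message does mention a week, but for a different behaviour: "each Sunday, we will ask you about your seatbelt use in the past week".

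**The same item elsewhere.** In Appendix: Screening Questions it sits under a heading that dates it: "The following questions ask you to recall times you have been in a car over the past 2 weeks". The text scripts carry no such heading.

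**Who receives it.** Section 2.3 admits people to Cohort 3 on "Any vehicle trip in past 2 weeks where individual reports driving a vehicle within 3 hours after consuming 3 or more drinks". Section 4.2.2 confirms that all participants had the risk at baseline.

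**How the answers are used.** Section 4.2.3 models the weekly SMS risk reports with GEE. For a missing week-8 or week-14 assessment it states: "If a participant has reported that risk via SMS weekly reports, we will use those values for missing weeks". If a week is still missing, it takes the worst value from the weeks before or after. In the intervention script the answer also selects the feedback message.

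**The concern.** A repeated measure of recent behaviour needs a stated recall window. At screening this item had one. In the weekly texts the window is left to be inferred from the preceding question.

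Three readings are open to a participant: the past week, the two weeks used when they met the same words at screening, or any time. Under the last, Yes remains true for every Cohort 3 participant because of what they reported to get in. Under the two-week reading, an event before the ED visit could still produce a Yes at the first check-in.

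Three uses are exposed:

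- **Slopes.** Change from pre-enrolment through run-in, intervention and follow-up (section 3.1.4) is flattened for anyone who answers literally. Section 2.10 also relies on the run-in to detect change after enrolment.
- **Filled-in outcomes.** A literal Yes becomes a week-8 or week-14 risk, and the worst-neighbour rule can carry it into an adjacent missing week.
- **Feedback.** In the intervention arm, the printed script offers no other risk answer from which to judge whether a weekly goal was met.

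**Working it through.** **1. Wording side by side (Cohort 3)**

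| Item | Period stated? |
|---|---|
| Screening item | Yes, two weeks, by heading |
| Weekly question on any driving | Yes, past week |
| Weekly risk item, run-in and intervention | No |
| Reminders for the risk item, both scripts | No |
| Run-in welcome message | Past week, but for seat belts |

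No separate control script is printed. Section 2.13 says controls continue the weekly assessments for 12 more weeks without feedback, so I take the run-in wording to apply to them throughout.

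**2. How many week-8 outcomes could be filled from texts**

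The documents give attrition only for Cohort 1 (section 4.1): 10% lost in the run-in and 80% completing week 8. The plan's own figure reproduces: 300 × 0.90 × 0.80 = 216, or 108 per arm.

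Applying the same rates to Cohort 3 is an assumption:

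- randomised: 100 × 0.90 = 90
- without a week-8 survey: 90 × 0.20 = 18

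This is an upper figure. Some people who miss the survey will also have missed texts. Section 4.2.1 removes anyone with no SMS response during the intervention period.

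**3. Effect of literal answers**

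Let p be the true weekly risk in an arm. Let f be the share of event-free participants who are recorded as Yes. People reporting no driving never receive the item, which holds f down. Then

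observed risk = p + (1 − p) × f

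and, with the same f in both arms,

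observed difference = (1 − f) × true difference.

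For an assumed 40% against 25% (15 points):

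| f | Observed risks | Observed difference |
|---|---|---|
| 0 | 40% vs 25% | 15 points |
| 0.10 | 46% vs 32.5% | 13.5 points |
| 0.25 | 55% vs 43.75% | 11.25 points |
| 0.50 | 70% vs 62.5% | 7.5 points |

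If f differed by arm, the error would not be pure dilution. With a true risk of 40% in both arms and f of 0.20 in controls and 0.10 in the intervention arm, observed risks are 0.40 + 0.60 × 0.20 = 52% and 0.40 + 0.60 × 0.10 = 46%. That is a spurious 6-point gap.

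Every value of p and f here is assumed; the documents supply none.

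**The case against.** The strongest reply is that the item never stands alone. It arrives on a Sunday, directly after a question about driving in the past week, and only if the answer was not 0. That filter makes little sense unless the follow-on concerns the same week. The preceding question uses the same *have you driven* form, so tense alone does not make the risk item open-ended. The belt and typing follow-on texts also lack a window, so Cohort 3 differs from them in degree. In the intervention arm, goals are set for the coming week, which frames the next check-in. All of this stands, and it makes ambiguity with some misclassification the right description.

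A reader might infer that participants can truthfully answer Yes every week. The documents do not support that: a week with no reported driving never reaches the item, and the context points many respondents to the past week.

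A reader might also infer that the run-in script rejects Yes, because only a reply to No is printed. That should not be held against the plan. The table is visibly broken, the reminder invites either answer, and the reply to unreadable texts says "Please text us either Yes or No".

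Consequences are limited too. Cohort 3 is exploratory (section 2.1), and so is the slope analysis. The main week-8 and week-14 outcomes come from web surveys under a two-week heading, and texts enter only where a survey is missing. Section 4.2.3 accepts a conservative direction for imputed weeks. That covers absent answers, however, and does not justify leaving an answered question open to misreading.

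**Conclusion.** The concern holds as a point of ambiguous measurement. The Cohort 3 weekly risk item and its reminders have no period of their own, although the same item at screening did, and all recipients had reported the behaviour before entry. Context will lead many to the intended week, but the script does not secure it.

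Any literal Yes affects the SMS slopes and the feedback branching directly. It affects the week-8 and week-14 outcomes only through filled-in values: at week 8, at most about 18 of 90 randomised, if Cohort 1's attrition carries over. The misreading rate is unknown, so the size of any bias cannot be stated. The (1 − f) dilution assumes equal misreading in both arms. No powered comparison is touched. The change is still worth making, because Cohort 3 has its own primary outcome and a planned main manuscript (section 10).

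**What to change.** Before enrolment, open the risk item in both Cohort 3 scripts (run-in/control and intervention) with *In the past week, have you driven…* and leave the rest unchanged. Put the same phrase in the reminders, including the run-in reminder that now asks only for a Yes or No. Use the dated wording in the assessment-only weeks after the intervention as well, so that the series is measured identically to week 14.

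Optionally, add the phrase to the belt and typing follow-on texts for consistency.

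The cost is a few words per message. Section 2.12 already has all queries written before enrolment, so the edit fits there. Made mid-trial, it would break the comparability of the weekly series.

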Appendix: SMS Interventions: Seat belt Safety

Day & Time	Incomin	Outroing
Day & Time Qualified Week 3,	g	Outgoing
Monday, 5pm		
Qualified		Congratulations [Name]! You have qualified to continue the SaVE Study For the next 6 weeks, we will help you set goals and provide you personalized feedback on your seat belt use We will check in next Sunday. Until then, take care
Week 3-8: Sunday, 3pm		
2 hours 2 hours	[Missing] x1 [Missing] x2 [Nonsen se]	Hi [_NAME_], it's the SaVE Study Team checking in How often have you been a passenger or driver in a car the past week? 0=never; 1=a few times; 2=most days; 3=every day We missed your response. Text us how often you have been a passenger or driver in a car the past week? You must be busy. We will check in next week We don't understand. Please text us a response option: 0=never; 1=a few times; 2=most days; 3=every day
1 hour	0 1,2,3 [Missing] x1	OK When in the car, how often did you wear a seat belt? 0=never; 1=a few times; 2=most of the time; 3=every time We missed your response. Text us how often you wore a seat belt
1 hour	[Missing] x2 [Nonsen se]	You must be busy. We will check in next week We don't understand. Please text us a response option: 0=never; 1=a few times; 2=most of the time; 3=every time
If Goal Not Set	3	[Posiitve Reinforcement Message]
	0,1,2	[Social Norms Message]
If Goal Set	Goal met Goal not met	[Goal Met Message] [Goal Not Met Message]
		Would you be willing to commit to a goal to wear a seat belt every time this week?
1 hour	[Missing] x1 [Missing]	We missed your response. Text us whether you'd be willing to set a goal?
1 hour	x2 [Nonsen se]	You must be busy. We will check in next week We don't understand. Please text us either yes or no
No Goal	No	[No Goal Roll Library Message]
Goal +	Yes	[Goal Reinforcement Message]
Random 2 days per week, 4pm		
lf goal -		[Seat belt Safety Info Message]
lf goal +		[Goal Reminder Message]

Appendix: SMS Interventions: TWD Safety

	Incomi	
Day & Time	ng	Outgoing
Qualified Week 3, Monday, 5pm		
Qualified [At least 1 Sunday Assessment complete]		Congratulations [Name]! You have qualified to continue the SaVE Study
· · · · · · · · · · · · · · · · · · ·		For the next 6 weeks, we will help you set goals and provide you personalized feedback on your driving safety
		We will check in next Sunday. Until then, take care.
Week 3-8: Sunday, 3pm		
2 hours	[Missin g] x1	Hi [_NAME_], it's the SaVE Study Team checking in. How often have you driven a car the past week? 0=never; 1=a few times; 2=most days; 3=every day We missed your response. Text us how often you have been a passenger or driver in a car the past week?
2 110013	[Missin	car the past week:
2 hours	g] x2 [Nonse nse]	You must be busy. We will check in tomorrow. We don't understand. Please text us a response option: 0=never; 1=a few times; 2=most days; 3=every day
1 hour	0 1,2,3 [Missin g] x1	OK. When driving, how often did you type on your phone when the car was moving? 0=never; 1=a few times; 2=most of the time; 3=every time We missed your response. Text us how often did you type on your phone while the car was moving
Thou	[Missin	was moving
1 hour	g] x2 [Nonse nse]	You must be busy. We will check in tomorrow. We don't understand. Please text us a response option: 0=never; 1=a few times; 2=most of the time; 3=every time
If Goal Not Set	0	[Posiitve Reinforcement Message]
	1,2,3	[Social Norms Message]
If Goal Set	Goal met Goal	[Goal Met Message]
	not met	[Goal Not Met Message]
		Would you be willing to commit to a goal to refrain from typing on your phone while driving this week?
1 hour	[Missin g] x1 [Missin	We missed your response. Text us whether you'd be willing to set a goal?
1 hour	g] x2 [Nonse	You must be busy. We will check in later.
	nse]	We don't understand. Please text us either yes or no
No Goal	No	[No Goal Roll Library Message]
Goal +	Yes	[Goal Reinforcement Message]
Random 2 days per week, 4pm		
lf goal -		[Distracted Driving Info Message]
If goal +		[Goal Reminder Message]

SaVE Trial Protocol v.1.0 Page **31** of **36**

Incoming	Outgoing
	Congratulations [Name]! You have qualified to continue the SaVE Study
	For the next 6 weeks, we will help you set goals and provide you personalized feedback on your driving safety
	We will check in next Sunday. Until then, take care
	Hi [_NAME_], it's the SaVE Study Team checking in
	How often have you driven a car the past week? 0=never; 1=a few times; 2=most days; 3=every day
[Missing] x1	We missed your response. Text us how often you driven a car the past week?
[Missing] x2	You must be busy. We will check in tomorrow
[Nonsense]	We don't understand. Please text us a response option: 0=never; 1=a few times; 2=most days; 3=every day
0	ОК
1,2,3	Have you driven a vehicle within 3 hours after consuming 3 or more alcoholic drinks?
[Missing] x1	We missed your response. Text us whether you have driven within 3 hours of drinking 3 or more alcoholic beverages.
[Missing] x2	You must be busy. We will check in next week
[Nonsense]	We don't understand. Please text us Yes or No.
No	[Posiitve Reinforcement Message]
Yes	[Social Norms Message]
Goal met	[Goal Met Message]
Goal not met	[Goal Not Met Message]
	Would you be willing to commit to a goal to not drive after drinking this week?
[Missing] x1	We missed your response. Text us whether you'd be willing to set a goal?
[Missing] x2	You must be busy. We will check in next week
[Nonsense]	We don't understand. Please text us either yes or no
No	[No Goal Roll Library Message]
Yes	[Goal Reinforcement Message]

Appendix: SMS Interventions: Drink Driving Safety

[Drink Driving Info Message]

[Goal Reminder Message]

Appendix: 8-Week Assessment

	been in a car over the past 2 weeks.				
Questi on	How often have you driven a car?	Never	A few times	Most days	Every day
Code	driver	0	1	2	3
Questi on	How often did you wear a seat belt when you drove a car?	Never	A few times	Most of the time	Always
Code	drive_seatbelt	0	1	2	3
Questi on	How often have you been a passenger in the front seat of a car?	Never	A few times	Most days	Every day
Code	pass_front	0	1	2	3
Questi on	How often did you wear a seat belt when you were a passenger in the front seat ?	Never	A few times	Most of the time	Always
Code	pass_seatbelt1	0	1	2	3
Questi on	How often have you been a passenger in the back seat of a car?	Never	A few times	Most days	Every day
Code	pass_back	0	1	2	3
Questi on	How often did you wear a seat belt when you were a passenger in the back seat?	Never	A few times	Most of the time	Always
Code	pass_seatbelt2	0	1	2	3
Questi on	How often did you type on your phone while you were driving and when the car was moving?	Never	A few times	Most of the time	Always
Code	distract	0	1	2	3
Questi on	What's the most number of alcoholic drinks you've had prior to driving on any occasion?	#			
Code	drinks	#			

The following questions ask you to recall times you have been in a car over the past 2 weeks.

Questi on	Check off all the reasons you have not used a seat belt	Uncomfort able	Forgot	Don't think they help	Like freedom	Other	l alway s wear my seat belt	
Code	seatbelt reasons	0	1	2	3	4	5	
Questi on	lf other, state reasons							
Code	seatbelt_other							
Questi on	How often do your friends use their seat belt?	Never	Rarely	Most of the time	Always			
Code		0	1	2	3			
Questi on	How dangerous is it to not wear a seat belt?	Not at all	Somew hat	Very	Comple tely			
Code	danger_seatbelt	0	1	2	3			
Questi on	How much do you agree: I have complete control over whether I wear a seat belt.	Strongly Disagree	Disagre e	Somew hat Agree	Mostly agree	Stron gly Agree		
Code	control_sb	0	1	2	3	4		
Questi on	Check off all the reasons you have typed on your phone while driving?	l could not wait	l don't think it affects my driving	It was an emerge ncy	It is fun	l get bored drivin g	l do not use my phon e while drivin g	l do not dri ve
Code	twd reasons	0	1	2	3	4	9 5	6
Questi on	How often do your friends type on their phones while driving?	Never	Rarely	Most of the time	Always			
Code		0	1	2	3			

SaVE Trial Protocol v.1.0 Page **33** of **36**

Questi on	How dangerous is it to type on your phone while driving?	Not at all	Somew hat	Very	Comple tely			
Code	danger_twd	0	1	2	3			
Questi on	How much do you agree: I have complete control over whether I type on my phone while driving.	Strongly Disagree	Disagre e	Somew hat Agree	Mostly agree	Stron gly Agree		
Code	control_twd	0	1	2	3	4		
Questi on	Check off all the reasons you have driven a car after drinking alcohol?	l had no other opiton	l don't think it affects my driving	lt's not a big deal	l am careful	lt is fun	l do not drive after dirnki ng alcoh ol	l do not dri ve
Code	dd reasons	0	1	2	3	4	5	6
Questi on	How often do your friends drive after drinking alcohol?	Never	Rarely	Most of the time	Always			
Code	friends_dd	0	1	2	3			
Questi on	How dangerous is it to drive soon after drinking more 3 or more alcoholic drinks?	Not at all	Somew hat	Very	Comple tely			
Code	danger_dd	0	1	2	3			
Questi on	How much do you agree: I have complete control over whether I type on my phone while driving.	Strongly Disagree	Disagre e	Somew hat Agree	Mostly agree	Stron gly Agree		
Code	control_dd	0	1	2	3	4		

Questi on	Did you find the text message program helpful?	Not at all	Somew hat	Very much
Code	helpful	0	1	2
Questi on	Would you recommend the program to others?	No	Yes	
Code	recom	0	1	
Questi on	Any other comments you'd like to provide that could help us make the text message program better?			
Code	comments			

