2.14 Outcome Assessments & Blinding

The primary outcomes will be the percentage of participants in each treatment arm who report vehicle risks at week 8 (immediate effects) and week 14 (durable effects). Questions are the same as those used in screening. Participants will receive a text prompting them to log in to the secure web site to complete the 21-question survey which should take them no more than 10 minutes to complete. Research associates and investigators will be blinded to the allocation until outcome evaluation. It is not possible to blind subjects given the nature of the intervention. We do not expect any scenarios where emergency unblinding will be necessary.

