2.18 Study flow diagram

3. OUTCOMES

3.1 Definitions

3.1.1 Primary Outcome

-Percentage of participants who report a vehicle risk at week 8.

- d. Cohort 1: Any vehicle trip in past 2 weeks where individual reports not using a seat belt
- e. Cohort 2: Any vehicle trip in past 2 weeks where individual reports phone was used to type while driving and car was moving
- f. Cohort 3: Any vehicle trip in past 2 weeks where individual reports driving a vehicle within 3 hours after consuming 3 or more drinks

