Appendix: SMS Run-In: Seat belt

Appendix: SMS Run-In: Typing While Driving (TWD)

Day & Time	Incomin g	Outgoing
Enrollment		Hi [_NAME_]. Welcome to to the SaVE Study
		For the next 2 weeks, each Sunday, we will ask you about your seatbelt use in the past week
		If you complete at least 50% of the text queries, you will be eligible for the rest of the study
	Any	
	respons e	If at any time you wish to stop receiving texts, just text us "stop"
Sunday,		
4pm		Hi [_NAME_], it's theSaVE Team checking in
		How often have you driven a car the past week? 0=never; 1=a few times; 2=most days; 3=every day
	[Missing	We missed your response. Text us how often you have been a passenger or driver in a car
2 hours] x1	the past week?
0 haven	[Missing	Veu must be busy. We will check in most week
2 hours] x2 [Nonsen	You must be busy. We will check in next week We don't understand. Please text us a response option: 0=never; 1=a few times; 2=most
	se]	days; 3=every day
	0	OK.

	1,2,3 [Missing	When driving, how often did you type on your phone when the car was moving? 0=never; 1=a few times; 2=most of the time; 3=every time We missed your response. Text us how often you typed on your phone when the car was				
1 hour] x1 [Missing	moving				
1 hour] x2 [Nonsen se]	You must be busy. We will check in next week We don't understand. Please text us a response option: 0=never; 1=a few times; 2=most of the time; 3=every time				
	0,1,2,3	Thanks				
Day 15 (Monday)		Due to your low response rate, you will be withdrawn from the SaVE Study				
	For further information about safe vehicle use, go to www.NHTSA.gov					

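### Cohort 2's primary outcome counts any typing trip, but the item that measures it has no exact answer for a single lapse, so some participants at risk may be recorded as risk-free, with bias of unknown direction

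*Combined protocol and SAP*

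**What the plan says.** Section 3.1.1 defines the Cohort 2 primary outcome at week 8 as "Any vehicle trip in past 2 weeks where individual reports phone was used to type while driving and car was moving". Section 2.3 uses the same definition for entry. One such trip is enough to count as risk.

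The survey item behind it is "How often did you type on your phone while you were driving and when the car was moving", with answers *Never* (0), *A few times* (1), *Most of the time* (2) and *Always* (3). It appears in this form in the screening, 8-week and 14-week appendices. For this item, the statement in section 2.14 holds: "Questions are the same as those used in screening".

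The weekly texts repeat the steps. The run-in script asks "how often did you type on your phone when the car was moving? 0=never; 1=a few times", and the intervention script asks "When driving, how often did you type on your phone when the car was moving? 0=never; 1=a few times; 2=most of the time; 3=every time". Section 4.2.3 uses these texts when a web assessment is missing: "If a participant has reported that risk via SMS weekly reports, we will use those values for missing weeks".

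Each weekly dialogue opens with a gate question. In Cohorts 2 and 3 it is "How often have you driven a car the past week? 0=never; 1=a few times; 2=most days; 3=every day". Cohort 1 has the same answer steps for being a passenger or driver. A reply of 0 receives an acknowledgement, and the risk question follows only a reply of 1, 2 or 3.

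No rule for turning the item into the binary outcome is written. The outcome definition implies a cut at 0 versus 1-3. So does the intervention script, which gives positive reinforcement for 0 and a social-norms message for 1-3 when no goal is set.

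**The concern.** The outcome threshold is one trip, and the answer scale has no step for one. A participant who slipped once must pick between *Never*, which is untrue, and *A few times*, which is imprecise. The two answers fall on opposite sides of the primary cut, so the participant's reading of the label decides the outcome. The analysis cannot later tell which *Never* answers hid a single lapse.

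Other items in the same instruments do not have this problem. The question "How often do your friends type on their phones while driving" includes *Rarely*. The Cohort 3 screening item is Yes/No. The seat-belt item is cut at *Always*, so one lapse fits *Most of the time*.

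Participants are not blinded (section 2.14). For six weeks the intervention arm is invited to commit to no typing and receives feedback on its weekly answer, while the control arm receives none. The two arms may therefore round a single slip differently. The Cohort 2 comparison at week 8 and week 14, and the weekly risk reports used for the slope analysis, all rest on this item.

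**Working it through.** **The plan's own figures.** There is no sample-size figure for Cohort 2. The Cohort 1 figures reproduce: 25% versus 10%, two-sided 0.05 and 80% power give 100 per arm, and 300 × 0.9 × 0.8 = 216. This point changes neither. If Cohort 1's attrition applied to Cohort 2 (an assumption), 100 × 0.9 × 0.8 = 72 would have week-8 data, or 36 per arm.

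**Formula.** In each arm let P(any) be the true share with at least one typing trip in 2 weeks, P1 the share with exactly one, and r the share of those who answer *Never*.

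- Recorded risk = P(any) − r × P1.
- Recorded risk reduction (control minus intervention) = true reduction + r_int × P1_int − r_ctl × P1_ctl.
- With equal r, the shift is r × (P1_int − P1_ctl). Its sign depends only on which arm has more single-lapse participants.

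**Inputs.** All trip distributions and values of r below are assumptions. For Poisson counts with mean m, P(any) = 1 − e^(−m) and P1 = m × e^(−m). For the negative binomial with k = 1, P(any) = 1 − 1/(1 + m) and P1 = m/(1 + m)². In the other rows P(any) is set directly, and P1 is a stated share of it.

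**Results.** Risk reductions are in percentage points. The odds ratio (OR) is for risk, intervention versus control.

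| Assumed scenario (control, intervention) | True | r = 0.25 | r = 0.5 | OR, true to r = 0.5 |
|---|---|---|---|---|
| Poisson means 4, 2 | 11.7 | 16.6 | 21.6 | 0.119 to 0.157 |
| Poisson means 3, 1.5 | 17.3 | 22.0 | 26.6 | 0.182 to 0.222 |
| Poisson means 3, 2 | 8.6 | 11.6 | 14.6 | 0.335 to 0.383 |
| Negative binomial, k = 1, means 3, 2 | 8.3 | 9.2 | 10.1 | 0.667 to 0.655 |
| Poisson means 1, 0.5 | 23.9 | 22.2 | 20.6 | 0.378 to 0.393 |
| Risk 90%, 75%; single-lapse share of those at risk 20%, 40% | 15.0 | 18.0 | 21.0 | 0.333 to 0.352 |
| Risk 90%, 75%; shares 20%, 20% | 15.0 | 14.25 | 13.5 | 0.333 to 0.487 |
| Risk 90%, 75%; shares 20%, 10% | 15.0 | 12.4 | 9.8 | 0.333 to 0.581 |
| Risk 90%, 90%; shares 20%, 40% | 0 | 4.5 | 9.0 | 1 to 0.603 |

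Worked example, Poisson 3 versus 1.5: P1 is 0.149 in control and 0.335 in intervention, so at r = 0.5 the shift is 0.5 × (0.335 − 0.149) = 0.093, and 17.3 becomes 26.6. For Poisson 1 versus 0.5: P1 is 0.368 and 0.303, so the shift is 0.5 × (0.303 − 0.368) = −0.032, and 23.9 becomes 20.6.

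The shift in the risk difference therefore runs from about −5 to about +10 points. In the four Poisson rows and the 20%/40% row with a true effect, the odds ratio moves toward 1 even where the risk difference grows.

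**Unequal rounding.** With no true effect, P1 = 15% in each arm, and r = 60% in intervention against 30% in control, the recorded difference is 0.15 × (0.60 − 0.30) = 4.5 points.

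**The case against.** The strongest reply is that *A few times* classifies a single lapse correctly. After one slip *Never* is plainly false, so many participants would round up, and those who do cause no bias. The item also asks how often the person typed, not on how many trips. Someone who typed several times on one trip fits *A few times*, so the affected group is closer to one typing act than one trip, and the model above can overstate it. Both arguments stand. They limit the size but do not remove the gap.

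The largest shifts need Poisson counts and 50% rounding. Overdispersed counts give less, as the negative binomial row shows. At 36 per arm the 95% half-width for 90% versus 75% is 1.96 × √(0.9 × 0.1/36 + 0.75 × 0.25/36) = 17.2 points, wider than any shift shown. Section 2.1 calls Cohort 2 exploratory. That limits the severity. But section 4.2.2 still plans a test at 0.05, and section 10 plans a separate main manuscript for the cohort.

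The unequal-rounding scenario is partly ordinary self-report bias, which a new label would not remove. The gate question matters less than the survey item, because the week-8 outcome comes from the web survey and texts replace it only when it is missing. Single-lapse patients missed at screening reduce yield and do not bias the randomised comparison.

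A reader might infer that rounding down always favours the arm with fewer lapses. The documents do not support that: they give no trip counts and no rounding rates, and the table shows plausible inputs under which that arm's advantage shrinks.

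**Conclusion.** The mismatch between outcome and item is in the text and recurs in every Cohort 2 instrument: one typing trip is a primary-outcome event, and no answer describes it. Some participants at risk may be recorded as risk-free.

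The direction is not known. It turns on which arm has more single-lapse participants, whether the unblinded intervention arm rounds down more, and whether the risk difference or the odds ratio is read; section 4.2.2 reports both. Under the assumed distributions and 25-50% rounding down, the risk difference shifts by a few points either way and by about 10 points in the extreme. If everyone rounds up, the shift is zero. All sizes rest on assumptions, and the documents cannot narrow them.

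Severity is minor to moderate, because Cohort 2 is exploratory and unpowered. The Cohort 1 survey outcome and sample size are unaffected. The change is worth making because it is nearly free and the lost information cannot be recovered in the analysis.

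**What to change.** 1. Keep the four codes of the typing item and relabel code 1 as *Once or a few times* at screening, week 8, week 14, and in the run-in and weekly texts.
2. State the scoring rule in section 3.1.1 or 4.2.2: 0 = no risk, 1-3 = risk.
3. Make the same label change to code 1 of the weekly driving or riding gate in all three cohorts' run-in and intervention scripts. A person with one trip who replies 0 is never asked the risk question, and Cohort 1 has the same gate.

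No code, branch, cut-point or sample size changes. The cost is label edits before enrollment. If they are made after enrollment has started, answers before and after differ slightly in meaning, so the date of change should be recorded. Relabelling does not remove deliberate under-reporting.
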